SECONDARY: Microbial translocation [Primarily, Lipopolysaccharide binding protein (LBP)], zinc level, oxidative markers, safety measures (% subjects with >Grade 2 adverse events possibly or probably to study drugs), lipid levels, insulin resistance (HOMA-IR), endoPAT, and blood pressure.

Design and Outcomes:

This is a pilot open labeled randomized double arm study, studying the efficacy and safety of Zinc therapy on cardiovascular outcomes in ≥ 18 years old HIV-infected patients, on stable ART (for at least 12 weeks) and with zinc levels ≤ 0.75 mg/L in the last 60 days.

Subjects will be evaluated and data will be collected according to the following schedule:

Evaluation (Weeks)	Screen	Entry*	Wk 4	Wk 10	W 16 or premature study discontinuation
Written consent form	X				
Inclusion/exclusion	X				
Family history of CVD/diabetes/HTN		X			
CVD Risk Score		X			X
Targeted physical exam/weight/blood pressure	X	X	X	X	X
Compliance assessment/safety monitoring			X	X	X
Smoking, illicit drugs and alcohol status		X			X
Dietary logs and Activity status		X			X
Height	X				
Hematology/chemistries	X	X	X	X	X
Urine β -HCG (women)	X	X	X	X	X
Fasting lipoprotein profile		X			X
Fasting insulin, glucose, HOMA-IR		X			X
Plasma inflammation markers		X			X
Microbial translocation (IFAB, LBP)		X			X
Oxidative markers		X			X
Zinc levels	X	X			X
Calcium Score		X			
DEXA		X			
Endothelial function		X			X
Resting Energy Expenditure (REE)		X			X
Stored fasting plasma, serum, urine and stool ***	X	X	X	X	X

Intervention and Duration:

The duration of the study will be 16 weeks. Patients will be given zinc gluconate capsules at a dose of 45 mg, or 90 mg, elemental zinc daily for 16 weeks. No additional follow up will occur after 16 weeks.

Sample size and population:

The total sample size is 50 patients, 25 patients will be randomized to one (45 mg) capsules and 25 patients will receive two 45 mg capsules (or 90 mg).

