HOMA-IR ($r=0.58$; $p<0.0001$), sCD14 ($r=0.19$; $p=0.018$), sCD163 ($r=0.23$; $p=0.005$), hs-CRP ($r=0.30$; $p<0.0001$); IL-6 ($r=0.20$; $p=0.017$), and sTNF-RI (0.26; 0.0015). The study did not measure visceral abdominal fat or whole body measurements, but nonetheless support the hypothesis that central fat accumulation in HIV is linked to monocyte activation and systemic inflammation. The effect of zinc deficiency on body composition or metabolism is unknown.

HYPOTHESIS:

In this pilot exploratory study, our hypothesis is that short term, 16 week, zinc therapy will result in improvement in mechanisms postulated to play a role in the development and progression of HIV CVD. The endpoints are

- 1) improved serum pro-inflammatory cytokine profile
- 2) reduced oxidative stress and improved serum antioxidant status
- 3) Increased intestinal tight junctions with decreased microbial translocation

STUDY OBJECTIVES

PRIMARY: To examine whether zinc significantly affect inflammation markers in HIV-infected subjects, we will assess changes overtime in inflammation markers, and correlate these changes with changes in zinc levels

SECONDARY:

- To examine whether zinc significantly affect microbial translocation in HIV-infected subjects, we will assess changes overtime in microbial translocation markers, and correlate these changes with changes in zinc levels

-To assess the safety and tolerability of 16 weeks of zinc in HIV-infected subjects

-To ascertain whether zinc significantly affect oxidative stress in HIV-infected subjects, we will assess changes overtime in oxidative markers, and correlate these changes with changes in zinc levels

- To examine the effects of zinc on systemic blood pressure, lipid and glucose metabolism in HIV-infected subjects with good virologic control, and correlate these changes with those of inflammatory and oxidative markers

STUDY ENDPOINTS

PRIMARY: The primary inflammation markers will be sCD14, sTNF-RI, and high sensitivity C reactive protein (hs-CRP).

SECONDARY: Microbial translocation [Primarily, Lipopolysaccharide binding protein (LBP)], zinclevel, oxidative markers, safety measures (% subjects with >Grade 2 adverse events possibly or probably to study drugs), lipid levels, insulin resistance (HOMA-IR), endoPAT, and blood pressure.

INCLUSION CRITERIA:

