- For any Grade 4 toxicity (confirmed X 2 values for laboratory abnormalities) regardless of the cause, subjects will be taken off study drugs but will continue to be followed and undergo the evaluations as per schedule of events. Exceptions are asymptomatic elevation of indirect bilirubin in subjects receiving indinavir or atazanavir therapy, asymptomatic elevation of CPK, or elevations in lipid levels.

CRITERIA FOR PERMANENT STUDY DISCONTINUATION

-Request by the subject to withdraw

-At the discretion of the IRB

-Pregnancy or breast-feeding

[figure not shown]
-Request of the primary care physician if s/he thinks the study is no longer in the best interest of the subject.

STATISTICAL CONSIDERATIONS

The primary Aim of this pilot study is to demonstrate that oral dosing of zinc can impact a biological signature in patients with HIV. Biological signatures (hs-CRP, sCD14, sTNF-RI, LBP) will be assessed to determine if giving the natural product (zinc gluconate at 45 mg and 90 mg) to patients with HIV results in a meaningful change in the measure.

Inter-assay variability less than 15% are generally acceptable¹¹. To reduce this variability we will repeat each of these assays twice (run in duplicate) and compute average from the repeated assays performed in the same lab under same conditions conducted by the same technician. Given this set-up, the bioassays will efficiently quantify the biomarkers with less than 6% inter-assay variability which is substantially less than the general acceptable guidelines. Moreover, this inter-assay variability should be equivalent in both sets of measures obtained at baseline and after the Zinc supplementation.

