We hypothesize that the distribution of at least two of the four biomarkers of primary interest (hs-CRP, sCD14, sTNF-RI and LBP) will be shifted towards left after oral supplementation compared to the baseline distribution of the biomarker, see the Figure below. This shift/change in the distribution is primarily due to the location change of a biomarker. Since the random or nuisance variations are same (although nominal) in both distributions, we will perform hypothesis tests for the systematic change in the distributions due to the treatment. We will perform Kolmogorov–Smirnov (K-S) test for the differences in distributions and median test for location change. These tests will determine significant effects of zinc supplementation on the targeted biomarkers. The K-S and median tests are global test for overall significance. We will also look at the effect of zinc supplementation on individual level.

To elicit treatment effects on each individual, we will subtract baseline value of a biomarker from the post zinc supplementation measured value of the biomarker (post minus pre). The baseline subtracted values of biomarker will have either zero (no change), positive or negative values. The baseline corrected biomarker values are in continuous nature, basically the subtracted values on the real line. For measuring significance of treatment by controlling random errors, we will perform linear regression on the baseline corrected biomarker values. This analysis has similarity with the Microarray normalization method using iterative linear regression¹². The significant regression coefficient (intercept only) would indicate that the difference is due to the zinc supplement.

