Effect size consideration: As above, we previously stated that we will perform significance tests for the shift of distributions of biomarkers after the zinc supplementation using Kolmogorov-Smirnov (K-S) test. The amount of shift or effect size will be measured using Cohen's d value. For estimating the effect size, we used our statin study data as the preliminary data (NCT01218802). In the statin study the baseline mean (SD) of hs-CRP, log(sCD14), log(sTNF-RI), and LBP are 4.95(10.45), 7.71 (0.35), 7.46 (0.37), and 21.11(10.91), respectively. For each level of zinc supplementation (i.e. 45 mg or 90 mg zinc) we will compute the change in a biomarker by taking the difference of a biomarker measured before- and after- the zinc supplementation. For example, we will compute the difference in LBP measured at baseline and after the zinc supplementation. Similarly, differences will be computed for the other biomarkers. The sample size of 20 achieves 80% power to detect effect size (Cohen's $d = \text{mean difference}/\text{SD of differences}$) of 0.20 or higher using a paired t-test with a 0.10 one-sided significance level in at least two biomarker out of the four. For the combined sample size of $n=40$ (both doses combined), the estimated effect size should be higher than the threshold Cohen's $d = 0.20$. The effect size estimation is performed using nQuary Advisor 7.0 software¹⁵.

All analysis will be by intent to treat. All subjects, regardless of whether they remain on study drug, will continue to be followed throughout the duration of the study. It is standard practice in the HIV studies where inflammation markers are measured, that every attempt would be made to schedule study visits during a time that subjects are not acutely ill. That would mean that a visit would be rescheduled if a patient shows up sick, as acute illnesses may affect inflammation markers. A period of >7 days ill-free would be required. This happens rarely overall but if it does in the setting of this study, participants would be asked to come back after illness resolves.

HUMAN SUBJECTS

Institutional Review Board (IRB) Review and Informed Consent

This protocol and the informed consent document and any subsequent modifications will be reviewed and approved by the University Hospitals Cleveland Medical Center CWRU IRB. A signed informed consent form will be obtained from each study subject. The informed consent form will describe the

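### LBP is a secondary endpoint in the objectives and endpoint lists, but counts as one of four primary markers in the hypothesis and power statement

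*Combined protocol and SAP*

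**What the plan says.** **Objectives and endpoints.** In both the précis and the protocol body, the primary objective concerns inflammation markers, and Study Endpoints reads "The primary inflammation markers will be sCD14, sTNF-RI, and high sensitivity C reactive protein (hs-CRP" with no fourth marker. LBP comes under the next heading: "SECONDARY: Microbial translocation [Primarily, Lipopolysaccharide binding protein (LBP)], zinc level, oxidative markers". The matching objective, "To examine whether zinc significantly affect microbial translocation in HIV-infected subjects", is also secondary.

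**Statistical Considerations.** The primary Aim is worded more broadly, as an effect of zinc on a biological signature, and "Biological signatures (hs-CRP, sCD14, sTNF-RI, LBP) will be assessed" for it. The hypothesis is that "at least two of the four biomarkers of primary interest (hs-CRP, sCD14, sTNF-RI and LBP) will be shifted towards left". Under Effect size consideration, power is given for a paired t-test at a "0.10 one-sided significance level in at least two biomarker out of the four".

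**Hypothesis section.** The overall hypothesis has three strands. One is "Increased intestinal tight junctions with decreased microbial translocation", alongside the cytokine profile and oxidative stress.

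**The concern.** The primary objective asks whether zinc affects inflammation. Under the statistics section, that question can be answered partly by a marker the protocol assigns to a different, secondary objective. Whether the primary objective is reported as supported may then depend on which list the author follows, and the protocol backs both.

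The blinding does not prevent a choice made after the results are known. Arm A/arm B coding hides the dose, but the planned tests compare week 16 with baseline, so marker results are visible whatever the coding. In addition, the categorical analysis in Statistical Considerations equates a negative change in a biomarker with less inflammation, so a fall in LBP could be given that label.

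**Working it through.** **1. The two lists**

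| Place | Primary markers | LBP | Count rule |
|---|---|---|---|
| Study Objectives and Study Endpoints (précis and body) | sCD14, sTNF-RI, hs-CRP | secondary | none |
| Statistical Considerations (Aim, hypothesis, power) | hs-CRP, sCD14, sTNF-RI, LBP | one of the four | at least two of four |

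Four markers give six possible pairs. Three of the six contain LBP.

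**2. The plan's power figure**

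Inputs from Effect size consideration: n = 20, d = 0.20, paired t-test, one-sided 0.10, stated power 80%; combined doses n = 40. Per-marker power is p = P(T > t(0.90, n−1)), where T is noncentral t with noncentrality d√n.

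- n = 20: noncentrality 0.20 × √20 = 0.894, p = 0.342.
- n = 40: noncentrality 0.20 × √40 = 1.265, p = 0.488.

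With independent markers:

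- Two of four: 1 − (1−p)⁴ − 4p(1−p)³
- Two of three: 3p²(1−p) + p³

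| All markers at d = 0.20 | n = 20 | n = 40 |
|---|---|---|
| Two of four | 0.423 | 0.669 |
| Two of three | 0.271 | 0.482 |

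The stated 80% is therefore not reproduced for two of four at n = 20. At least one of four would give 1 − 0.658⁴ = 0.813, but that is not the stated rule. The shortfall is a separate matter. What counts here is that any restated power depends on the list.

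**3. All markers null (p = 0.10)**

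- Two of four: 1 − 0.6561 − 0.2916 = 0.0523.
- Two of three: 0.027 + 0.001 = 0.028.
- LBP plus exactly one other: 3 × 0.1² × 0.9² = 0.0243, which is 46% of 0.0523.

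**4. Only LBP responds (d = 0.20), the other three null**

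Two of four is met with probability p(1 − 0.9³) + (1−p)(0.028).

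- n = 20: 0.342 × 0.271 + 0.658 × 0.028 = 0.111.
- n = 40: 0.488 × 0.271 + 0.512 × 0.028 = 0.147.
- Two of three stays at 0.028.

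**5. Correlated markers**

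The documents give no correlations, so a common correlation of 0.3 to 0.7 is assumed and simulated.

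| Scenario | Two of four | Two of three |
|---|---|---|
| All null | 8.2% to 10.6% | 5.0% to 8.0% |
| Only LBP at d = 0.20, n = 20 | 14% to 16% | 5% to 8% |
| Only LBP at d = 0.20, n = 40 | 17% to 18% | 5% to 8% |
| All at d = 0.20, n = 40 | 62% to 56% | about 49% |

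Under the null, the share that depends on LBP falls to 39% at correlation 0.3 and 25% at 0.7.

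**6. Effect size needed for 80% on the count (independent markers)**

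Two of three needs per-marker power 0.713, so d is about 0.42 (n = 20) or 0.29 (n = 40). Two of four needs 0.582, so d is about 0.34 or 0.24.

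**The case against.** The strongest reply is that two of three is not in the protocol. If the primary objective counted as supported when any one of the three listed markers moved, the null rate would be 1 − 0.9³ = 27.1% with independent markers, and about 24% to 19% at correlation 0.3 to 0.7. Two of four would then be the stricter rule, and it would still be stricter if only LBP responded (11% or 15%, against 27%). That stands: the figures illustrate the ambiguity but do not establish which way it would push a result. The null rate for two of four is also not clearly above the 0.10 used per marker.

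It can also be said that this is an exploratory pilot, that two of four is a hypothesis and power condition rather than a success criterion, that each marker is analysed separately so all four results would be seen, and that the statistics section uses its list consistently. The overall hypothesis lends that list some support by including microbial translocation. All of this is fair and limits the consequence. It does not remove the contradiction: the protocol states a hypothesis, tests and a power claim for its primary Aim on a marker set that its own endpoint section does not recognise.

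**Conclusion.** The concern holds. The primary set is three markers in one part of the protocol and four in another, and LBP plus one inflammation marker satisfies the stated hypothesis. Compared with two of three, counting LBP changes power at d = 0.20 by 15 points (n = 20) or 19 points (n = 40) with independent markers. When only LBP responds, it raises the chance of meeting the count from 2.8% to 11% or 15%.

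These sizes rest on one-sided 0.10 t-tests as in the power statement, since no level is given for the planned K-S, median and regression tests. They also rest on my two-of-three comparator and on assumed correlations. The contradiction itself needs none of these assumptions.

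**What to change.** Use one primary list in the objective, endpoint, hypothesis and power text, and state the count rule on it before any marker results are seen. The procedures for Study Entry have samples batched and assayed at the end of the study, which leaves room to do this.

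- **Option A, consistent with the primary objective.** Limit the hypothesis to sCD14, sTNF-RI and hs-CRP with a stated count, for example at least two of three (a proposed rule). Report LBP as the leading secondary endpoint, outside the count.
- **Option B.** Amend the objective and endpoint sections so that LBP is primary, and keep two of four.

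Either way, restate power for the chosen rule, with the assumed correlation given.

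The cost is protocol wording and a new power sentence; no new data are needed. The drawback of Option A is lower stated power at d = 0.20: the 15 or 19 points above if markers are independent, narrowing at correlation 0.7 to about 6 points (39% against 33%, n = 20) and 7 points (56% against 49%, n = 40).

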Further, for individual level impact of zinc supplementation, we will create categorical variable from the baseline subtracted biomarker values. Let's denote the number of positive, negative, and no change biomarker values by n_1 , n_2 , and n_3 , respectively, for a biomarker. Note that the total sample size $n = n_1 + n_2 + n_3$. From this count we will compute proportions of positive, negative, and no changes. We hypothesize that most of the subtracted values will be negative. Since we want to look at the benefit of supplementation, we will compare the proportions of negative values to the proportions of positive values using McNemar's test statistic¹³. For this moderate sample size without placebo trial, we will estimate the 90% confidence interval for the proportions difference using Agresti and Min¹⁴ methods. We will also perform logistic regression analysis on the binary change (positive vs negative) to estimate the odds ratio for the benefit of zinc supplementation. From the estimated logistic regression model will be able to predict probability of negative change (reduction in inflammation) for receiving zinc supplementation.

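### The tests said to decide significance (K-S and an undefined median test) are not the paired t-test that sizes the trial; on the natural reading K-S ignores the pairing, and no deciding test is named

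*Combined protocol and SAP*

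**What the plan says.** All of this is in the Statistical Considerations section of the combined protocol and SAP.

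- **K-S and median tests.** The plan compares the biomarker distribution after zinc with the baseline distribution: "K-S) test for the differences in distributions and median test for location change. These tests will determine significant effects of zinc supplementation". It adds: "The K-S and median tests are global test for overall significance". The Effect size paragraph repeats the role: "we will perform significance tests for the shift of distributions of biomarkers after the zinc supplementation using Kolmogorov-Smirnov (K-S) test".
- **Regression on post minus pre.** This is introduced as the individual-level look, but it also receives a significance role: "For measuring significance of treatment by controlling random errors, we will perform linear regression on the baseline corrected biomarker values", and "The significant regression coefficient (intercept only) would indicate that the difference is due to the zinc supplement".
- **Direction of change.** Also at individual level, "we will compare the proportions of negative values to the proportions of positive values using" McNemar's statistic, and "we will estimate the 90% confidence interval for the proportions difference". A logistic regression follows.
- **Sizing.** The Effect size paragraph bases 20 patients per dose (40 for both doses combined) on a paired t-test at one-sided 0.10, with success in two or more of four biomarkers.
- **Success rule.** The hypothesis concerns "the distribution of at least two of the four biomarkers of primary interest": hs-CRP, sCD14, sTNF-RI and LBP. The Study Endpoints section names only the first three as primary and lists LBP as secondary.

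A level and sidedness are stated only for the paired t-test. The form of the median test is not stated.

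**The concern.** Two problems meet here.

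First, each patient supplies both a baseline and a week-16 value. A K-S test that treats the two sets as independent samples throws away the pairing on which the sample-size argument depends. If a patient's two values are positively correlated, as repeated biomarker values usually are, K-S rejects too rarely. A real reduction that the sizing test would detect can then be missed by the test said to decide.

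Second, several analyses may each be read as establishing significance, and the plan does not say which one settles the question or how K-S and the median test combine. The same data could be reported as positive or negative according to a choice made after the results are seen. This matters for a pilot whose stated primary aim is to demonstrate a biological effect and which sets a formal two-of-four rule.

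**Working it through.** **1. The plan's own figure.** Inputs from the Effect size paragraph: n = 20, d = 0.20 (mean difference over SD of differences), one-sided 0.10, stated power 80%. Paired t-test: critical value 1.328 on 19 df, noncentrality d√n = 0.20 × √20 = 0.894, power 34.2%. If all four markers shift by d = 0.20 and are independent, at least two of four gives 1 − 0.658⁴ − 4 × 0.342 × 0.658³ = 42.3%. The stated 80% is not reproduced. That is a separate issue, but it means the tests must be compared at two effect sizes: the protocol's 0.20, and 0.485, where the paired t-test does have 80% (0.485 × √20 = 2.169).

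**2. The paired t-test is already planned.** With change scores dᵢ and only an intercept, the estimate is the mean of dᵢ, its standard error is s_d/√n, and t = mean(d)/(s_d/√n) on n − 1 df. That is the paired t-test.

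**3. Why K-S is conservative under pairing.** The one-sided statistic is the largest value of F_post(x) − F_base(x). For independent samples of equal size, P(nD ≥ k) = C(2n, n−k)/C(2n, n). At n = 20, k = 7 gives C(40,13)/C(40,20) = 0.087, while k = 6 gives 0.168, so the test rejects at D ≥ 7/20. With positively correlated pairs the variance of F_post(x) − F_base(x) is reduced by the covariance term, but the critical value stays the same.

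**4. Size and power by simulation.** Assumptions not in the documents: normal data, correlation r between 0.3 and 0.8, one-sided 0.10 for every test. The shift is d√(2(1−r)) baseline SDs. At r = 0 the simulated K-S size is 8.7%, matching the exact value.

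| n = 20 | r = 0.3 | 0.5 | 0.7 | 0.8 |
|---|---|---|---|---|
| K-S size (paired t 10%) | 6% | 4% | 2% | 1% |
| K-S power, d = 0.485 (paired t 80%) | 59–60% | 47% | 29% | 17% |
| K-S power, d = 0.20 (paired t 34%) | 20–21% | 14–15% | 7% | 4% |
| K-S and paired t disagree, d = 0.485 | 25% | 35% | 52% | 63% |

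At n = 40 and d = 0.339 (paired t 80%), K-S has 57 / 45 / 26 / 14%. If K-S were run two-sided at 0.05 instead, with n = 20 and d = 0.660 (two-sided paired t 80%), it has 48 / 32 / 14 / 6%. The direction does not depend on the assumed level.

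**5. The undefined median test and combination rule.** At n = 20, d = 0.485, take the median test as an exact sign test on differences (reject at 14 of 20 or more, size 5.8%). If either it or K-S may reject, power is 70 / 66 / 60 / 58%; if both must, 45 / 37 / 24 / 15%. A two-sample median test alone has 44 / 33 / 19 / 12%. The missing definitions therefore move the answer a good deal.

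**6. Choosing among tests afterwards.** With no effect and n = 20, counting a marker as positive if any of paired t, K-S or sign test rejects gives about 12–14% per marker (r from 0.8 down to 0), against 10%.

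**The case against.** **The plan is not without structure.** It calls K-S and median global and introduces the regression and McNemar analyses as individual-level. That ordering stands as far as it goes. It does not settle the matter, because the regression is also said to measure significance and no rule covers disagreement.

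**The words two-sample do not appear.** Correct. The two-sample form is inferred from comparing the post-treatment with the baseline distribution. No paired or permutation version is described.

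**The power contrast depends on the benchmark.** Partly. Part of the fall in K-S power across correlations comes from holding d fixed in SDs of differences: at d = 0.485 the shift drops from 0.485 × √1.4 = 0.57 to 0.485 × √0.4 = 0.31 baseline SD. At a fixed shift of 0.5 baseline SD, K-S stays at 47–50% while the paired t-test has 72–99%. The ranking is unchanged. For skewed raw hs-CRP (assumed lognormal with the protocol's mean 4.95 and SD 10.45) the gain is small at r = 0.3 (62% against 59%) but large at 0.8 (58% against 18%).

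**Stronger readings that a reader might infer.** One is that ignoring the pairing raises false positives. Under positive correlation it does the reverse; the excess comes only from choosing among tests, and it is modest. Another is that the McNemar comparison is anti-conservative. Its uncorrected form has a size of 13.2% at n = 20 only if one-sided 0.10 is assumed. The plan gives no level for it, and at one-sided 0.05, which matches the 90% interval, it rejects at 14 of 20 with size 5.8%.

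**It is an exploratory pilot.** True, and this limits the severity, but the plan still sets formal tests and a success rule.

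**Conclusion.** The point holds and should be fixed. The test described as deciding is not the sizing test, on its natural reading it ignores the pairing, and the plan names no deciding test, no rule for disagreement, no level for K-S or the median test, and no form for the median test. These textual gaps need no assumption.

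The size of the loss does rest on assumptions: positive within-patient correlation of 0.3 to 0.8, normal data and one-sided 0.10. On those, following the plan literally at n = 20 costs from about 20 to more than 60 percentage points of power where the paired t-test has 80%, and from about 13 to 30 points at d = 0.20.

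A reader might infer that naming the paired t-test brings the trial back to its stated 80% power. It does not: at d = 0.20 per-marker power is 34% with 20 patients and 49% with 40.

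**What to change.** First reconcile the marker set: the Statistical Considerations section counts LBP among four biomarkers of primary interest, while the Study Endpoints section names three primary markers and lists LBP as secondary. A two-of-four rule cannot be finalised until that is settled.

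Then add SAP text along these lines, assuming the four-marker set is confirmed:

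*For each marker the deciding test is the one-sided 0.10 paired t-test on week 16 minus baseline, that is, the intercept of the planned change-score regression, on the scale used in the Effect size paragraph (log for sCD14 and sTNF-RI, raw for hs-CRP and LBP). The aim is met if at least two of the four show a significant reduction. The rule applies [to each dose arm / to both doses combined / to both, stating which decides]. K-S comparisons are descriptive. All other tests are supportive and do not alter the conclusion.*

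If a median test is kept, define it as an exact sign test on within-patient differences and label it supportive. This is the same test as an exact McNemar comparison of negative with positive changes, so it should appear once.

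The cost is wording only. The deciding analysis is already planned, and no extra patients, visits or assays are needed. The shortfall in power at d = 0.20 needs its own correction.
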